9.3. Populations for Analyses

The following populations are defined (Table 6):

Table 6: Populations for Analyses

Population	Description	
Enrolled Set	All participants who sign the ICF	
Safety Set	All participants who receive at least 1 dose of study intervention	
Pharmacokinetic/Pharmacodynamic	All participants who have sufficient plasma samples to have evaluable PK	
(PK/PD) Analysis Set	data for bupropion and total Mo (as a measure of ALXN1840) in plasma	

Abbreviation: ICF = informed consent form; Mo = molybdenum.

9.4. Statistical Analyses

Statistical methods described in this section will be further elaborated in a separate Statistical Analysis Plan (SAP). The SAP will be developed and approved before database lock and will describe the participant populations to be included in the analyses, and procedures for accounting for missing data.

Summary statistics will be computed and displayed by study group and by visit, where applicable. Descriptive statistics for continuous variables will include number of non-missing values, arithmetic mean, standard deviation, median, minimum, and maximum. Categorical variables will be summarized using percentages and frequency counts.

All statistical analyses will be conducted using SAS® for Windows® Version 9.3 or higher.

9.4.1. Efficacy Analyses

No efficacy analyses will be performed for this study.

9.4.2. Safety Analyses

All safety analyses will be performed on the Safety Set.

Safety analyses will include an analysis of all AEs, ECGs, clinical laboratory data, physical examinations, and vital sign measurements using descriptive statistics. Data will be summarized by study groups.

No inferential statistical analyses are planned for the safety parameters of this study. The incidence of AEs and SAEs will be summarized by System Organ Class (SOC) and Preferred Term for each treatment and overall, and by relationship to study intervention. Adverse events will also be summarized by treatment and overall by severity. Serious AEs and AEs resulting in withdrawal from the study will be listed. Participants having multiple AEs within a category (eg, overall, SOC, Preferred Term) will be counted once in that category. For severity tables, a participant's most severe event within a category will be counted.

Changes from baseline in vital sign measurements and laboratory assessments (eg, chemistry, blood cell count with differential, and urinalysis) will be summarized by study groups. Laboratory parameter values will be graded according to the National Cancer Institute Common Terminology Criteria for Adverse Events (CTCAE). Shift tables by treatment will be produced for these laboratory parameters. These tables will summarize the number of participants with each baseline grade relative to the reference ranges and changes to the worst highest grade assessed postdose during the study.

Electrocardiogram parameters will be measured at the specified time points, including heart rate, PR, RR, QRS, QT, and corrected QTcF intervals. The average of the triplicate ECG readings at the time points collected will be calculated, and changes from pretreatment baseline values will be assessed by each treatment.

All concomitant medications will be coded and summarized using the World Health Organization (WHO) Drug Dictionary.

9.4.3. Other Analyses

9.4.3.1. Pharmacokinetic and Pharmacodynamic Analyses

Pharmacokinetic analyses will be performed using the PK/PD Analysis Set.

Blood samples for PK analysis of total Mo (as a measure of ALXN1840), bupropion and its metabolite, hydroxybupropion will be collected at the following time points: pre-dose and post-dose at 1, 2, 3, 4, 5, 6, 8, 12, 24, 48, 72, 96, 120, 144, 168, 192, 216, 240, and 336 hours in each period (Note: the 336 hours sample in Period 1 will be collected during the Period 2, Pre-dose [Day 1] Visit).

The following plasma PK parameters will be calculated as endpoints for total Mo, bupropion and hydroxybupropion using noncompartmental methods with Phoenix WinNonlin (Certara USA Inc., Princeton, New Jersey) Version 8.0 or higher or SAS Version 9.3 or higher (SAS Institute Inc., Cary, North Carolina), as applicable. Calculations will be based on the actual sampling times recorded during the study.

- Time delay between the time of dosing and time of appearance of drug concentration in plasma (T_{lag}; for plasma total Mo with ALXN1840 administration)
- Maximum observed concentration in plasma (C_{max})
- Time to $C_{max}(T_{max})$
- Area under the plasma concentration (AUC) versus time curve from time 0 to the last quantifiable concentration (AUC_t)
- AUC versus time curve from time 0 to infinity (AUC∞)
- AUC extrapolated from time t to infinity as a percentage of total AUC_∞ (%AUC_{extrap})
- Apparent terminal-phase elimination rate constant (λ_z)
- Terminal elimination half-life (t_{1/2})
- Apparent oral clearance (CL/F)
- Apparent volume of distribution (V_d/F)
- Metabolite to parent ratio based on AUC (MRAUC) and C_{max} (MRC_{max}) [estimated for bupropion and hydroxybupropion]

Additional plasma PK parameters may be calculated if deemed appropriate.

Plasma concentrations of total Mo, bupropion and hydroxybupropion and time deviation data will be presented in a data listing by participant. Plasma concentration data will be summarized

separately by analyte and time point for each treatment using the following descriptive statistics: number of participants, arithmetic mean, SD, coefficient of variation (CV), median, minimum, and maximum. Mean plasma concentration versus scheduled time profiles will be presented in figures on both linear and semilogarithmic scales. Individual plasma concentration versus actual time profiles will be presented similarly.

Pharmacokinetic parameters derived from plasma concentrations of total Mo, bupropion and hydroxybupropion will be presented in data listings and summarized separately using the following descriptive statistics: number of participants, arithmetic mean, SD, arithmetic CV, median, minimum, maximum, and 95% CI. Geometric mean and geometric CV will be presented for C_{max} and AUCs only.

The effect of ALXN1840 on the bupropion PK will be assessed using a linear mixed-effect model (SAS PROC MIXED) with treatment condition, sequence, and period as fixed effects and participant nested within sequence as a random effect. The model will be fitted to the natural-log-transformed PK parameters C_{max} , AUC_{∞} and AUC_t for estimation of effects and construction of CIs for the test treatment (Treatment B: 150 mg bupropion + 60 mg ALXN1840) compared with the reference treatment (Treatment A: 150 mg bupropion). The within-participant CV for the corresponding PK parameters will be estimated using the mean squared error from the statistical model. Confidence intervals (90%) will be constructed for the least-squares geometric mean ratio (GMR) estimates between the test and reference treatments for above PK parameters using the natural log-transformed data. The GMR estimates and the associated 90% confidence limits will be exponentiated back to the original scale. These analyses will be repeated to assess the effect of ALXN1840 on hydroxybupropion PK.

Analyses of other PK data including, but not limited to PUF Mo may be conducted.

Pharmacodynamic data of ALXN1840 including, but not limited to, plasma total Cu, Cp, CpC, and potentially toxic Cu measured as LBC and PUF Cu and/or assessed via NCC/NCC corrected may be analyzed and reported.

Details of the PK/PD analyses will be described in the PK/PD data analysis plan or included in the SAP, which will be finalized before database lock.

9.5. Interim Analyses

No interim analyses are planned for this study.

9.6. Data Monitoring Committee

There will not be a Data Monitoring Committee, but provision is included for an ad hoc Safety Review Committee (SRC), if needed.

9.7. Safety Review Committee

To ensure participant safety, ad hoc SRC meetings may be held to discuss urgent issues should the need arise. The ad hoc SRC must convene within 24 hours in the case of a TESAE or the withdrawal of any participant due to an adverse reaction.

The ad hoc SRC, consisting of the Investigator, Alexion Safety Physician and Alexion Medical Monitor will evaluate the study data, if needed, for participant safety and make recommendations on termination of the study.

10. SUPPORTING DOCUMENTATION AND OPERATIONAL CONSIDERATIONS

10.1. Appendix 1: Regulatory, Ethical, and Study Oversight Considerations

10.1.1. Regulatory and Ethical Considerations

- This study will be conducted in accordance with the protocol and with the following:
 - Consensus ethical principles derived from international guidelines including the Declaration of Helsinki and Council for International Organizations of Medical Sciences (CIOMS) International Ethical Guidelines
 - Applicable International Council for Harmonisation (ICH) Good Clinical Practice (GCP) Guidelines
 - Applicable laws and regulations
- The protocol, protocol amendments, ICF, IB, and other relevant documents (eg, advertisements) must be submitted to an IRB/IEC by the Investigator and reviewed and approved by the IRB/IEC before the study is initiated.
- Any amendments to the protocol will require IRB/IEC approval and, where applicable, competent authority approval before implementation of changes made to the study design, except for changes necessary to eliminate an immediate hazard to study participants.
- The Investigator will be responsible for the following:
 - Providing written summaries of the status of the study to the IRB/IEC annually or more frequently in accordance with the requirements, policies, and procedures established by the IRB/IEC.
 - Notifying the IRB/IEC of SAEs or other significant safety findings as required by IRB/IEC procedures.
 - Providing oversight of the conduct of the study at the site and adherence to requirements of 21 Code of Federal Regulations (CFR), ICH guidelines, the IRB/IEC, European regulation 536/2014 for clinical studies (if applicable), and all other applicable local regulations.

10.1.2. Financial Disclosure

Investigators and Sub-Investigators will provide Alexion with sufficient, accurate financial information as requested to allow Alexion to submit complete and accurate financial certification or disclosure statements to the appropriate regulatory authorities. Investigators are responsible for providing information on financial interests during the course of the study and for 1 year after completion of the study.

10.1.3. Informed Consent Process

- It is the responsibility of the Investigator to obtain signed (written or electronic signature) informed consent from all study participants prior to any study-related procedures including screening assessments.
- The Investigator or his/her representative will explain the nature of the study (including but not limited to the objectives, potential benefits and risk, inconveniences, and the participant's rights and responsibilities) to the participant, defined according to local and country regulations where the study is taking place, and answer all questions regarding the study.
- Participants must be informed that their participation is voluntary. Participants, or their legally authorized representative, will be required to sign a statement of informed consent that meets the requirements of 21 CFR 50, local regulations, European Union (EU) General Data Protection Regulation (GDPR), ICH guidelines, Health Insurance Portability and Accountability Act (HIPAA) requirements, where applicable, and the IRB/IEC or study center.
- The medical record must include a statement that written informed consent was obtained before the participant was screened in the study and the date the written consent was obtained. The authorized person obtaining the informed consent must also sign the ICF(s).
- Participants must be re-consented to the most current version of the ICF(s) during their participation in the study.
- A copy of the signed (written or electronic) documentation (ie, a complete set of participant information sheets and fully executed signature pages) must be provided to the participant or the participant's legally authorized representative, as applicable. This document may require translation into the local language. Signed (written or electronic) consent forms must remain in each participant's study file and must be available for verification at any time.
- The ICF will contain a separate section that addresses the use of remaining mandatory samples for optional exploratory research. The Investigator or authorized designee will explain to each participant the objectives of the exploratory research. If sharing exploratory research results with the Investigator is not planned, the ICF should mention it. Participants or legally authorized representative will be told that they are free to refuse to participate and may withdraw their consent at any time and for any reason during the storage period. A separate signature will be required to document a participant's agreement to allow any remaining specimens to be used for exploratory research. Participants who decline to participate in this optional research will not provide this separate signature.

10.1.4. Data Protection

• Participants will be assigned a unique identifier by Alexion. Any participant records or datasets that are transferred to Alexion will contain the identifier only; participant

names or any information which would make the participant identifiable will not be transferred.

- The participant must be informed that his/her personal study-related data will be used by Alexion in accordance with local data protection law. The level of disclosure must also be explained to the participant who will be required to give consent for their data to be used as described in the informed consent.
- The participant must be informed that his/her medical records may be examined by Clinical Quality Assurance auditors or other authorized personnel appointed by Alexion, by appropriate IRB/IEC members, and by inspectors from regulatory authorities.

10.1.5. Dissemination of Clinical Study Data

Study-related information and study results may be posted on publicly accessible clinical study databases (eg, the US website www.clinicaltrials.gov or the EU website www.clinicaltrialregister.eu), as appropriate, and in accordance with national, regional, and local regulations.

10.1.6. Data Quality Assurance

- All participant data relating to the study will be recorded on a printed or electronic CRF unless transmitted to Alexion or designee electronically (eg, laboratory data). The Investigator is responsible for verifying that data entries are accurate and correct by physically or electronically signing the CRF.
- The Investigator must maintain accurate documentation (source data) that supports the information entered in the CRF.
- The Investigator must permit study-related monitoring, audits, IRB/IEC review, and regulatory agency inspections and provide direct access to source data documents.
- Alexion or its designee is responsible for the data management of this study including quality checking of the data.
- Study monitors will perform ongoing source data verification to confirm that data entered into the CRF by authorized site personnel are accurate, complete, and verifiable from source documents; that the safety and rights of participants are being protected; and that the study is being conducted in accordance with the currently approved protocol and any other study agreements, ICH GCP, and all applicable regulatory requirements.
- Records and documents, including signed ICFs, pertaining to the conduct of this study must be retained by the Investigator for 2 years after the last marketing application approval, or if not approved, 2 years following the discontinuance of the test article for investigation, unless local regulations or institutional policies require a longer retention period. No records may be destroyed during the retention period without the written approval of Alexion. No records may be transferred to another location or party without written notification to Alexion.

10.1.7. Source Documents

Source documents provide evidence for the existence of the participant and substantiate the integrity of the data collected. The Investigator or designee will prepare and maintain adequate and accurate source documents (eg, medical records, ECGs, AE and concomitant medication reporting, raw data collection forms) designed to record all observations and other pertinent data for each participant.

Data reported in the CRF that are transcribed from source documents must be consistent with the source documents or the discrepancies must be explained. The Investigator may need to request previous medical records or transfer records, depending on the study. Also, current medical records must be available. Source documents are filed at the Investigator's site.

10.1.8. Study and Site Start and Closure

The study start date is the date on which the first participant signs the informed consent.

Alexion or its designee reserves the right to close the study site or terminate the study at any time for any reason at the sole discretion of Alexion. Study sites will be closed upon study completion. A study site is considered closed when all required documents and study supplies have been collected and a study site closure visit has been performed.

The Investigator may initiate study site closure at any time, provided there is reasonable cause and sufficient notice is given in advance of the intended termination.

Reasons for the early closure of a study site by Alexion or the Investigator may include but are not limited to:

- Failure of the Investigator to comply with the protocol, the requirements of the IRB/IEC or local health authorities, Alexion 's procedures, or GCP guidelines.
- Inadequate recruitment of participants by the Investigator.
- Discontinuation of further study intervention development.

If the study is prematurely terminated or suspended, Alexion shall promptly inform the Investigators, the IECs/IRBs, the regulatory authorities, and any contract research organization(s) used in the study of the reason for termination or suspension, as specified by the applicable regulatory requirements. The Investigator shall promptly inform the participant and should assure appropriate therapy and/or follow-up.

10.1.9. Publication Policy

- Where possible, primary manuscripts reporting results of the primary efficacy endpoint or the final results will be submitted for publication within 12-18 months of the primary evaluation date or end of study, whichever is earlier.
- Investigators who participate as authors in manuscripts derived from Alexion-sponsored studies will agree to the prerequisites as outlined in the Alexion author engagement agreement prior to engaging in manuscript development.
- The Investigator agrees to submit proposals for new manuscripts (whether or not the proposed analyses are derived from protocol-specified endpoints) to Alexion for

review and consideration. All manuscripts or abstracts emanating from approved proposals are to be submitted to Alexion for review before submission to the journal/society. This allows Alexion to protect proprietary information and to provide comments.

- The proprietary nature of some development work may preclude publication. In some cases, it may be necessary to delay a publication to allow Alexion to ensure protection of intellectual property.
- In general, primary publications, including congress and journal publications, containing the protocol-specified results of a study should occur prior to the publication of individual study site results or case reports. Alexion's policy prohibits duplicate publication, whereby the same results must not be published in multiple peer-reviewed journal manuscripts.
 - Encore congress publications may be appropriate to allow communication of research findings to relevant audience and geographical regions.
- Alexion will comply with the requirements for publication of study results. In accordance with standard editorial and ethical practice, Alexion will generally support publication of multicenter studies only in their entirety and not as individual site data. In this case, a coordinating Investigator will be designated by mutual agreement.
- Authorship will be determined by mutual agreement and in line with International Committee of Medical Journal Editors authorship requirements and per the Alexion Publication Policy.

10.2. Appendix 2: Clinical Laboratory Tests

- The tests detailed in Table 7 be performed by the local laboratory.
- Protocol-specific requirements for inclusion or exclusion of participants are detailed in Section 5 of the protocol.
- Additional tests may be performed at any time during the study as determined necessary by the Investigator or required by local regulations. Investigators must document their review of each laboratory safety report and indicate whether out of range results are clinically significant ("CS") or not clinically significant ("NCS").
- Women of childbearing potential should only be enrolled after a negative serum pregnancy test result at screening. Additional urine pregnancy testing will be standard for the protocol unless serum testing is required by site policies, local regulation, or IRB/IEC and should be performed per the time points specified in the SoA (Table 1). Screening pregnancy criteria are detailed in Section 5.1.

Table 7: Protocol-Required Safety Laboratory Assessments

Laboratory Assessments	Parameters			
Hematology	Platelet Count Red blood cell count Hemoglobin Hematocrit	RBC Indices: Mean corpuse Mean corpuse % Reticulocy	cular volume cular hemoglobin	WBC count with differential: Neutrophils Lymphocytes Monocytes Eosinophils Basophils
Clinical Chemistry	BUN Potassium Bicarbonate Sodium Glucose AST ALT Chloride		Alkaline phosphatase Direct bilirubin Total bilirubin Albumin Creatinine Creatine phosphokinase	
Coagulation	INR Partial thromboplastin time Prothrombin time			
Routine Urinalysis	Specific gravity pH Glucose Protein Blood Bilirubin Urobilinogen Nitrite Leukocyte esterase by d Microscopic examination			

Table 7: Protocol-Required Safety Laboratory Assessments

Laboratory Assessments	Parameters
Other Screening Tests	Urine alcohol and urine drug screen (to include at minimum: amphetamines, barbiturates, benzodiazepines, cocaine, opiates, phencyclidine, methamphetamine, 3,4-methylenedioxy-methamphetamine, methadone, and tetrahydrocannabinol [cannabinoids])
	Human immune deficiency virus (HIV)-1 and HIV-2 antibodies, HbsAg ^a , anti-HBC IgG + IgM (if IgG positive), and anti- HCV with confirmation by HCV RNA Serum or urine hCG pregnancy test (as needed for women of childbearing potential) FSH (postmenopausal females only)

Note: All events of ALT \geq 3 × upper limit of normal (ULN) and bilirubin \geq 2 × ULN (> 35% direct bilirubin) or ALT \geq 3 × ULN and international normalized ratio (INR) > 1.5, if INR measured which may indicate severe liver injury (possible Hy's Law), must be reported as an SAE (excluding studies of hepatic impairment or cirrhosis).

^a Only HBsAg testing is necessary for exclusion of active HBV infection; anti-HBC laboratory collection is not required.

Abbreviations: ALT = alanine aminotransferase; AST = aspartate aminotransferase; BUN = blood urea nitrogen; FSH = follicle-stimulating hormone; HbsAg = hepatitis B surface antigen; HbA1C = hemoglobin A1C; HBC = hepatitis B core antigen; hCG = human chorionic gonadotropin; HCV = hepatitis C virus; HIV = human immunodeficiency virus; Ig = immunoglobulin; INR = international normalized ratio; RBC = red blood cell; RNA = ribonucleic acid; WBC = white blood cell.

Investigators must document their review of each laboratory safety report.

10.3. Appendix 3: Adverse Events: Definitions and Procedures for Recording, Evaluating, Follow-up, and Reporting

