2.3.1. Risk Assessment

Details of the potential risks and mitigation strategy are provided in Table 2.

Table 2: Potential Risks and Mitigation Strategy

Potential Risk of Clinical Significance	Summary of Data/Rationale for Risk	Mitigation Strategy
ALXN1840		
Dose-dependent elevations in transaminases (ALT and AST)	Generally mild to moderate in severity, asymptomatic and reversible with dose adjustments were reported, usually after 3 - 6 weeks of treatment in patients with WD	Regular monitoring of liver function tests
Anemia	Anemia has been observed in patients with WD, PBC and cancer, attributed to overtreatment and resultant Cu depletion	Monitoring complete blood count
Low white blood cell count (leukopenia, bone marrow toxicity)	Leukopenia and bone marrow toxicity (myelosuppression) have been observed in patients with WD and attributed to overtreatment and resultant Cu depletion	Monitoring complete blood count
Study Procedures		
Risks associated with the study design and procedures	Participants will undergo repeated blood draws to measure the PK of the study intervention and metabolism. Blood draws may result in ecchymosis, redness and	Blood draws are optimized for PK. A cannula may be placed to minimize needle sticks

	minor pain to the site. On rare occasion, infection or thrombophlebitis can occur	
Bupropion		
As per prescribing information	Bupropion prescribing information (WELLBUTRIN SR)	Participants will be monitored for adverse reactions and by regular laboratory assessments. Participants may be discontinued for significant drug related adverse events

Abbreviations: ALT = alanine aminotransferase; AST = aspartate aminotransferase; Cu = copper; IB = Investigator's Brochure; PBC = primary biliary cholangitis; PK = pharmacokinetics; WD = Wilson Disease.

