5.2. Exclusion Criteria

Participants are excluded from the study if any of the following criteria apply:

Medical Conditions

- 1. History or presence of/significant history of or current cardiovascular, respiratory, hepatic, renal, gastrointestinal, endocrinological, hematological, neurological disorder, seizure disorder or eating disorder (anorexia or bulimia). Participants with a history of gastric bypass, other surgical procedure, or medical condition that may significantly alter absorption of drugs.
- 2. Clinically significant multiple or severe drug allergies, food allergies, or allergies to study product or class of product or its derivatives.
- 3. Lymphoma, leukemia, or any malignancy within 5 years of Screening, except for basal cell or squamous epithelial carcinomas of the skin that have been resected with no evidence of metastatic disease for 3 years.
- 4. Breast cancer within the past 10 years.
- 5. Serum creatinine > upper limit of normal (ULN) of the reference range of the testing laboratory at Screening or on Check-in Period 1.

- 6. Alanine aminotransferase (ALT), aspartate aminotransferase (AST), or total bilirubin > ULN of the testing laboratory at Screening and Check-in. Participants with confirmed Gilbert's syndrome may be included with total bilirubin > ULN but below 3 × ULN if participant has a measured direct bilirubin < ULN.
- 7. Current or chronic history of liver disease or known hepatic or biliary abnormalities (with the exception of Gilbert's syndrome or asymptomatic gallstones).
- 8. QTc > 450 msec for male participants or > 470 msec for female participants NOTE A: The QTc is the interval between the start of the Q-wave and the end of the T-wave in an ECG (QT interval) corrected for heart rate according to Bazett's formula (QTcB), Fridericia's formula (QTcF), and/or another method. It is machine-read with Investigator review.
 - NOTE B: The specific formula used to determine eligibility and discontinuation for an individual participant should be determined prior to initiation of the study; QTcF is preferred; however, QTcB may be used if QTcF cannot be measured.

Prior/Concomitant Therapy

- 9. Use or intended use of prescription medications (excluding oral contraceptives) within 14 days or 5 half-lives of the drug (whichever is longer) prior to dosing on Day 1, except with prior approval of Alexion. Participants may not have a medical condition that requires chronic medicinal therapy.

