7. DISCONTINUATION OF STUDY INTERVENTION AND PARTICIPANT DISCONTINUATION/WITHDRAWAL

7.1. Discontinuation of Study Intervention

In rare instances, it may be necessary for a participant to permanently discontinue (definitive discontinuation) the study intervention. If the study intervention is definitively discontinued, the participant should remain in the study to be evaluated for safety follow-up. See the SoA (Table 1) for data to be collected at the time of discontinuation of study intervention and follow-up.

Discontinuation of study intervention for abnormal liver function should be considered by the investigator if transaminase elevations (ie, AST or ALT) exceeds 3 × ULN or if the Investigator believes that it is in best interest of the participant.

If a clinically significant finding is identified (including, but not limited to QTcF \geq 500 ms or QTcB \geq 500 ms), the Investigator or qualified designee will determine if the participant can continue in the study and if any change in participant management is needed. Review of the ECG printed at the time of collection must be documented. Any new clinically relevant finding should be reported as an AE.

Participant should be considered for discontinuation from intervention if any of the following occur during the study:

- Serious hypersensitivity reaction;
- Severe uncontrolled infection;
- Use of disallowed medication;
- Pregnancy or planned pregnancy (see Section 10.4); or
- Alexion or the Investigator deems it is necessary for the participant.

See the SoA (Table 1) for samples and data to be collected at the time of study intervention discontinuation and follow-up and for any further evaluations that need to be completed.

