10.3.4. Reporting of SAEs

SAE Reporting to Alexion GDS via Paper Safety Reporting Form

- All SAEs will be recorded and reported to Alexion or designee immediately and within 24 hours awareness.
- SAEs will be reported using the Safety Reporting Form and submitted to Alexion Global Drug Safety (GDS). The Investigator must complete, sign, and date the SAE pages, verify the accuracy of the information recorded on the SAE pages with the corresponding source documents, and send a copy via email or facsimile to the contact information provided below:
 - Email: [contact] or Fax: [name]
- Additional follow-up information, if required or available, should be entered into the CRF and sent to Alexion GDS within 24 hours of the Investigator or study site staff becoming aware of this additional information via the reporting process outlined above.
- For all SAEs, the Investigator must provide the following:
 - Appropriate and requested follow-up information in the time frame detailed above
 - Causality of the SAE(s)
 - Treatment of/intervention for the SAE(s)
 - Outcome of the SAE(s)
 - Medical records and laboratory/diagnostic information
- All paper forms and follow-up information submitted to Alexion GDS **must** be accompanied by a cover page signed by the Investigator.
- Paper source documents and/or reports should be kept in the appropriate section of the study file.

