8.6. Other Safety Data

8.6.1. Liver Function Results

All events of ALT \ge 3 \times upper limit of normal (ULN) and bilirubin \ge 2 \times ULN (> 35% direct bilirubin) or ALT \ge 3 \times ULN and international normalized ratio (INR) > 1.5, if INR measured which may indicate severe liver injury (possible Hy's Law), must be reported as an SAE (excluding studies of hepatic impairment or cirrhosis).

Liver function results will be presented in a summary table and eDISH (evaluation of drug-induced serious hepatotoxicity) plots.

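### The mandatory SAE rule for possible Hy's law names ALT only; adding AST to both limbs is a cheap, minor improvement to safety reporting

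*Protocol*

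**What the plan says.** The rule is in the note to Table 7 (Protocol 10.2, Appendix 2). Its first limb begins "All events of ALT \geq 3 × upper limit of normal (ULN) and bilirubin \geq 2 × ULN (> 35% direct bilirubin". Its second is ALT ≥ 3 × ULN with INR > 1.5, where INR is measured. Either must be reported as an SAE. SAP 8.6.1 repeats both limbs, ending "which may indicate severe liver injury (possible Hy's Law), must be reported as an SAE". Neither document names AST in either limb.

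Three other places in the protocol pair the enzymes:

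- Table 2 (Section 2.3.1) lists as an ALXN1840 risk "Dose-dependent elevations in transaminases (ALT and AST").
- Exclusion criterion 6 (Section 5.2) begins "Alanine aminotransferase (ALT), aspartate aminotransferase (AST), or total bilirubin > ULN of the testing laboratory at Screening and Check-in".
- Section 7.1 asks the investigator to consider stopping study intervention "if transaminase elevations (ie, AST or ALT) exceeds 3 × ULN".

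Two consequences follow from SAE status. Section 10.3.4 states: "All SAEs will be recorded and reported to Alexion or designee immediately and within 24 hours awareness". Under Section 9.7 the committee "must convene within 24 hours in the case of a TESAE or the withdrawal of any participant due to an adverse reaction".

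**The concern.** The Table 7 note takes the reporting decision out of the investigator's hands for a laboratory pattern that may signal severe liver injury. Where the protocol describes the transaminase risk, screens for it, or prompts a stop, it uses both enzymes. Only the step that compels reporting drops AST, and no reason is given. If the same picture were led by AST with ALT below 3 × ULN, the rule would not fire, and by itself the pattern would start neither the 24-hour report nor the mandatory SRC meeting. What is at stake is the certainty and speed of escalation in a rare case. The bupropion comparison, the sample size and the PK analysis are not involved.

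**Working it through.** The plan gives no figure to reproduce. The check is a logical one, followed by a search for other routes.

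**The rule.** Automatic SAE = (ALT ≥ 3 × ULN and bilirubin ≥ 2 × ULN with > 35% direct) or (ALT ≥ 3 × ULN and INR > 1.5).

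| Pattern | Current rule | With ALT or AST |
|---|---|---|
| ALT ≥ 3 × ULN, any AST, bilirubin or INR condition met | SAE | SAE |
| ALT < 3 × ULN, AST ≥ 3 × ULN, bilirubin or INR condition met | not automatic | SAE |
| Either enzyme ≥ 3 × ULN, neither condition met | not automatic | not automatic |

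With ALT below 3 × ULN both limbs are false whatever AST, bilirubin and INR show. Only the second row changes, so the gap is confined to that row.

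**Other routes for the second row.**

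- *To an SAE:* a serious outcome such as hospitalization, or a judgment that the event is medically important; Section 10.3.2 says the latter should usually count as serious. Under 10.3.1 an abnormal result is an AE if the investigator judges it clinically significant.
- *To the SRC:* a resulting TESAE; withdrawal due to an adverse reaction, which does not itself make the event an SAE; or the general provision that "ad hoc SRC meetings may be held to discuss urgent issues should the need arise".
- *To the sponsor or Medical Monitor:* prompt discussion of immediate safety concerns (Section 8); notification of clinically significant values that do not resolve (8.2.4); review of all safety data before Day 11 discharge (Section 1.2), with Medical Monitor notice if there are clinically significant abnormalities then (4.1).
- *Section 7.1* only prompts consideration of stopping, and no dose remains to be stopped after Period 2 dosing.
- *Section 8.3.5* names no adverse events of special interest, so no such category fills the gap.

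Apart from serious outcomes and, for the SRC, withdrawal, each route needs someone to judge that the finding matters. None is automatic.

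**Whether the data exist.** AST, ALT, total and direct bilirubin and creatine phosphokinase are in the chemistry panel and INR is in the coagulation panel, drawn at the same visits (Table 1; SAP 8.2). Per participant after the first dose: Period 1 Days 2, 5, 10 (3) + Period 2 Check-in (1) + Period 2 Days 2, 5, 10 (3) + EOS (1) = 8. Over 52 participants completing both periods: 52 × 8 = 416. Panels after ALXN1840: sequence BA 26 × 8 = 208, sequence AB 26 × 4 = 104, total 312. At the amendment 31 were already randomized, leaving 52 − 31 = 21 and at most 21 × 8 = 168 panels if the change applied only to them. These are scheduled draws at which the rule could be applied. They say nothing about how many cases to expect.

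**The case against.** The strongest reply is that this is a preference rather than a defect. Table 2 describes a risk, exclusion 6 sets eligibility and Section 7.1 prompts a stopping decision; none defines an SAE. Using both enzymes there and ALT alone for possible Hy's law is not contradictory, and protocol and SAP agree. That stands. A reader might infer that the plan contradicts itself or breaches a requirement, and the documents do not support that.

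A reader might also infer that an AST-led case would go unnoticed or unreported. That goes too far. Six of the eight panels (Days 2, 5 and 10 of each period) fall while participants are in the unit, safety data are reviewed before discharge, and SAP 8.6.1 plans a liver function summary and eDISH plots, though without saying which transaminase they use. A participant screened for normal ALT, AST and bilirubin (Gilbert's syndrome excepted) who showed this pattern would be hard to overlook. These safeguards shrink the practical gap without making the report certain.

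It can be said that even the ALT rule leaves room for judgment, because Section 10.3.2 holds that an event that is not an AE cannot be an SAE. But the note is specific and mandatory for the ALT pattern, and no equivalent exists for AST.

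Finally, Table 2 describes elevations as generally mild to moderate, asymptomatic and reversible, usually after 3 to 6 weeks of treatment in patients with Wilson disease. It does not describe AST-led injury with raised bilirubin or INR. This supports a low rating.

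**Conclusion.** The point holds as a minor, inexpensive improvement to safety reporting. The uncovered pattern is AST ≥ 3 × ULN with ALT < 3 × ULN, plus bilirubin ≥ 2 × ULN (> 35% direct) or INR > 1.5, with no outcome that is itself serious. That pattern can still be escalated, but nothing makes escalation automatic. Few if any cases are expected: each participant receives one 60 mg dose, participants are screened healthy volunteers, and the elevations in Table 2 came mostly after weeks of treatment. No event rate is given, so none is calculated. The panel counts assume full completion and should not be read as a measure of risk. The PK results are unaffected.

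**What to change.** In the Table 7 note, write ALT or AST ≥ 3 × ULN in both limbs, and align SAP 8.6.1. The protocol wording is what governs site reporting; the SAP edit keeps the documents consistent. No new data are needed.

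Make the change in the next amendment, or sooner if the sponsor and IRB allow. Administrative Change Letter 1 added a Table 7 footnote, but that only clarified that a screening test was not required. Widening an SAE criterion is a different kind of change and may need full IRB approval (10.1.1), in which case it may reach few or none of the remaining participants.

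The downside is the rare muscle-origin AST rise that also meets the bilirubin or INR condition. It would require an SAE report and, if treatment-emergent, an SRC meeting. Creatine phosphokinase on the same panel can help interpret such a case, but the new wording makes no exception for it.
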